### **Analysis Plan**

Data analysis will include descriptive statistics to characterize the sample and inferential statistics to compare study variables. Sleep characteristics will be expressed as percent change from beginning to end and analyzed with repeat measures ANOVA. Blood levels will also be expressed as percent change from baseline to last draw. Correlational analysis will be used with sleep variables and IR. Regression analysis including components of sleep, BMI, dietary and physical activity will be conducted to examine the association of sleep factors and IR. Responses to the exit interview questions will be content coded and interrater reliability assessed.

- 3. Data and Safety Monitoring and Reporting: If there is an adverse or reportable event, the IRB will be notified promptly via the eIRB reportable event form. Also, the event will be documented in a tracking log. The sponsor does not require reporting above and beyond Emory IRB reporting requirements. This study does not include more than minimal risk; however, the PI will periodically review documentation to ensure accuracy and completeness.

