## **Objectives**

**Aims:** The aims for this pilot study of young adults ages 18-25 years old with IR (based on established cut points), short sleep (< 7 hours/night) and obesity (BMI  $\geq$  30) are to: 1) evaluate the feasibility and acceptability of a tailored intervention to extend sleep duration (SLEEP-Extend), 2) determine changes in sleep duration after SLEEP-Extend intervention, 3) evaluate IR levels before and after SLEEP-Extend, and 4) explore the potential mediators of diet and physical activity between sleep duration and IR. Our hypotheses are: H1: Individuals undergoing SLEEP-Extend will have longer sleep duration and increased knowledge of sleep hygiene post-intervention compared to controls and, H2: A greater proportion of the SLEEP-Extend group will have a decrease in IR compared to the control group.

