### **Outcome Measures:**

**BMI and baseline blood samples will be obtained at the screening visit.** All other measures will be assessed at the baseline visit and at the end of the 4-week intervention period except for the following: 1) Actigraphy watch will be worn continuously, and daily sleep diary completed for the entire study period, 2) The sleep hygiene pre/post-test and safety pre/post-test (control group only) will be given prior to intervention, immediately post intervention and at end of 4-week intervention period (3 time points), 3) Participant characteristics questionnaire only at baseline, and 4) Both groups will receive the exit survey at end of 4 week intervention period. **Insulin Resistance:** A) Glucose and insulin levels will be measured from fasting serum samples. B) Insulin Resistance will be calculated from the measured glucose and insulin levels using standard formulas. Briefly, serum samples will be collected via venipuncture and analyzed at Cardiovascular Specialty Laboratories, Inc (Atlanta, GA) using standard laboratory approaches with calibrated equipment (See letters of cooperation, from [name] and [name]). These two values will be used to calculate the homeostatic model assessment of insulin resistance (HOMA-IR; blood glucose level X insulin level, divided by 22.5). Elevated values indicate IR. A cutoff score of HOMA-IR < 2.1 as normal and HOMA-IR  $\geq$  2.1 as elevated (evidence of IR) will be used as determined in non-diabetics (Esteghamati et al., 2010). **Sleep Duration:** Using wrist actigraphy (Motionlogger, AMI, Ardsley, NY) along with a sleep diary (required to help validate and score actigraphy data; Martin & Hakim, 2011), we will objectively monitor each participant's 24-hour sleep-wake cycle to obtain average sleep duration (total sleep time) for one week (baseline) prior to random assignment to group and will continue monitoring during the 4 week intervention period. All participants wear the device (looks like a watch) on the wrist continuously for a total of 5 weeks (1 week for baseline sleep and 4 weeks of intervention period), except while bathing or swimming. Leproult and colleagues (2015) had success with adults wearing a wrist actigraph continuously for a total of 8 weeks. This device contains a light sensor that stores activity counts in 1-minute epochs and will detect the onset and offset of sleep using concurrent data from sleep diaries (Buysse et al., 2008; Morgenthaler et al., 2007). The Motionlogger was successfully validated against polysomnography on dimensions of sleep patterns: sleep onset latency, wake time after sleep onset, total sleep time (sleep duration), and sleep efficiency percentage (Cole et al., 1992). Data for each sleep component will be averaged over the 7 days for each week of the protocol (e.g. average sleep efficiency percentage, average total sleep duration) for analysis. Actigraphy has been compared to polysomnography to detect sleep and wakefulness and found to have a sensitivity of .965 and accuracy of .863 (Marino et al., 2013). The sleep diary is necessary to record data to help interpret actigraphy data (time in bed, time awake, and anything that occurs during the night such as waking up in the middle of the night). Participants in the SLEEP-Extend group will also use a daily sleep diary to record any sleep hygiene practices they use. Participants in the control group will use the same daily sleep diary as the SLEEP-Extend group with the difference of recording any safety practices used rather than recording sleep hygiene practices used. **Sleep Hygiene Knowledge:** To assess

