
## **Study Methods**

**Design:** A two-group, pre-test/post-test experimental design will be used to examine the feasibility and estimate the effects of a sleep intervention (SLEEP-Extend) designed to extend sleep duration in obese, young adults with short sleep and IR. Participants will wear actigraphy watches for one week of baseline sleep data and for an additional four weeks during the intervention.

**Sample/Setting:** We will recruit from Emory Hospital and Emory affiliated hospitals (Children's Healthcare of Atlanta, Emory St. Joseph's, Emory Johns Creek, Emory Midtown) through nursing staff email listservs as well as through flyers on Emory University campus and in areas that might attract young adults, through course web announcements, listservs for student emails and through social media, 20 obese individuals age 18-25 years old with short sleep (duration less than 7hrs./night) and evidence of IR [HOMA-IR levels  $\geq 2.1$  using serum sample (Esteghamati et al., 2010)] (See Timeline). We want to ensure 10 participants are in both groups; therefore, based on our previous experience recruiting from this age group, we will recruit individuals to give us a final N=20 (10 in each group).

Inclusion criteria: 1) Age 18-25 years old, 2) Self-report short sleep, 3) BMI  $\geq 30$  (the World Health Organization's classification of being obese, 4) IR determined by serum analysis, 5) Be willing to extend time in bed (See intervention below) by one hour total per night, and 6) Read and speak English.

Exclusion criteria (all self-report): 1) Night shift workers (circadian disruption can alter glucose and insulin levels), 2) Diagnosed sleep disorder (e.g., sleep apnea, restless leg syndrome,) which may impact glucose, insulin, and other hormones, 3) Medical diagnosis of diabetes or pre-diabetes, 4) Pregnant or lactating women or history of gestational diabetes, 5) Actively or intentionally trying to lose or gain weight (alteration of glucose metabolism/insulin secretion), 6) Hospitalization in past 3 months for medical or psychiatric condition, or 7) Major chronic disease (e.g., cancer, Lupus). The 5-week study will be conducted during the middle of the semester when the longer holidays and final exams do not occur.

1. Data samples will not be saved/banked or archived for future use.

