receive \$20 after one week of baseline data. At the end of the study, all participants will receive an additional \$30, a certificate of appreciation and a booklet on Healthy Sleep (NHLBI, 2011). Any participants that are noted to have additional risk factors for T2DM will be provided educational material on reducing T2DM risk factors and the suggestion made to follow up with a physician. After serum blood values are analyzed, all participants will be sent a letter with their glucose, insulin and HOMA-IR information along with a description of these values and recommendation for physician follow up. The principal investigator is a registered nurse who will collect the data and administer the sleep intervention. Standard universal precautions will be used during blood draws. Additionally, a GRA, also a registered nurse, will assist with data collection.

**Sample size:** A target sample size of 10 in the SLEEP-Extend group and 10 in the control will be used for this feasibility study (accounting for 20% attrition) given the need for a serum blood test as part of screening a number of participants to meet strict eligibility criteria. Participants will be randomly assigned to either the control or SLEEP-Extend group using a table of random numbers.

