- e. After one week of baseline actigraphy and pulse oximetry monitoring, the subject will return the actigraph and pulse oximeter and data will be downloaded and analyzed for sleep duration and oxygen saturation respectively. The researcher or GRA will access sleep diary information from the SleepBot app by taking a screen-shot of the data and printing it. Sleep diary info on the screen-shot will be deleted and only a paper version of the sleep diary will be retained. If the subject used a paper sleep diary, then it will be returned to the researcher for analysis.
- f. If the subject's average sleep duration is not below 7 hours per night or their insulin resistance level does not meet the inclusion criteria (HOMA-IR is a measure of insulin

resistance and needs to be  $\geq 2.1$  in order to meet inclusion criteria), or if their oxygen desaturation index is  $\geq 5$ /hour they will be thanked for their interest and told they are not eligible for the study. Additionally, if the subject's oxygen desaturation index is  $\geq 5$ /hour, they will be instructed to follow up with a health provider for assessment of possible OSA.

- g. If the subject's average sleep duration is less than 7 hours per night and their HOMA-IR meets inclusion criteria ( $\geq 2.1$ ) and their oxygen desaturation index is  $< 5$ /hour, then the subject will be scheduled for their study enrollment visit (Visit #2) to collect questionnaires/surveys. Subjects will be given \$10 after the screening visit.
5. Visit #2 (Study Enrollment Visit): This visit is done as soon as possible following screening. The researcher or GRA will meet the subject in a private room located on the university campus. The study enrollment visit for all subjects includes randomization to the treatment or control group and completion of:
  - a. Researcher-developed demographic/subject characteristics questionnaire
  - b. Baecke physical activity questionnaire
  - c. Dietary Screener questionnaire
  - d. Meal Timing questionnaire
  - e. Perceived Stress Scale
  - f. Sleep Hygiene Index questionnaire
  - g. Control group only: an investigator-developed safety practices questionnaire
  - h. Each subject will be asked to wear the actigraphy watch continuously for 4 additional weeks and complete daily sleep diary for 4 additional weeks (as previously discussed).
  - i. The intervention will be administered as follows

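### The sleep analysis pairs a one-value percent change with repeated-measures ANOVA and no baseline adjustment; a baseline-adjusted model in minutes with one named contrast would be clearer and usually more precise

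*Combined protocol and SAP*

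**What the plan says.** The Analysis Plan section gives one sentence on sleep: "Sleep characteristics will be expressed as percent change from beginning to end and analyzed with repeat measures ANOVA".

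The Outcome Measures section supplies the data. The actigraph is worn for five weeks ("1 week for baseline sleep and 4 weeks of intervention period"), and "Data for each sleep component will be averaged over the 7 days for each week of the protocol". Each completer therefore has one baseline and four intervention means.

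The hypothesis to be served is H1 in Objectives: "Individuals undergoing SLEEP-Extend will have longer sleep duration and increased knowledge of sleep hygiene post-intervention compared to controls".

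The sample-size paragraph under Procedures sets "A target sample size of 10 in the SLEEP-Extend group and 10 in the control", described as "accounting for 20% attrition". Study Methods says instead that "we will recruit individuals to give us a final N=20 (10 in each group".

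The documents do not say which weeks are the beginning and the end, whether percent changes or raw weekly means enter the ANOVA, which effect tests H1, or whether baseline sleep is adjusted for. They give no alpha, SD, between-week correlation, target gain in sleep or power.

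**The concern.** The two halves of the sentence do not fit together. Once sleep is reduced to one percent change per person, there is no within-person factor left for a repeated-measures ANOVA. Someone has to choose week, scale and effect later, possibly with the data in view.

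The two most direct ways out each lose something. Following the words literally leaves weeks 1–3 unused. Entering all five raw weekly means makes the group-by-week test an omnibus test that answers whether the arms differ in any pattern, not by how much. Neither uses baseline-week sleep as a covariate.

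Sleep duration is Aim 2 and part of H1, and the pilot is meant to lay the ground for a larger study. That study will need a group difference in minutes with a confidence interval. Percent change also gives the same gain different weight: 45 minutes is 12.5% of 360 but 10.7% of 420.

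**Working it through.** The plan contains no power or precision figure for sleep, so there is nothing to reproduce. The check compares analyses of the same five weekly means.

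**From the documents:** 5 weekly means; 2 arms; 10 per arm (8 if 10 is the recruited number and 20% are lost).

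**Assumed, because not given:** two-sided alpha 0.05 and a sleep gain of 45 min. The documents state only a time-in-bed instruction, which itself differs between the intervention overview (one hour) and the visit details (one to two hours).

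**Step 1, degrees of freedom.** With five raw means, group-by-week has (5−1)(2−1) = 4 df and error (20−2)(5−1) = 72. With only baseline and week 4, the interaction is the 1-df comparison of raw change.

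**Step 2, variance ratios.** Let weekly means have equal variance σ² and equal correlation ρ. The per-person variances are:
- change from baseline to week 4: 2σ²(1−ρ)
- week 4 adjusted for baseline: σ²(1−ρ²)
- mean of weeks 1–4 minus baseline: 5σ²(1−ρ)/4
- mean of weeks 1–4 adjusted for baseline: σ²(1−ρ)(1+4ρ)/4

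The first divided by the last is 8/(1+4ρ): 3.1 at ρ = 0.4, 2.4 at 0.6, 1.9 at 0.8, and never below 1.6. This does not depend on σ or the effect. At ρ = 0.6 it splits into 2/(1+ρ) = 1.25 from adjustment at week 4 and 4(1+ρ)/(1+4ρ) = 1.88 from averaging four weeks. With σ = 60 min (assumed) and 10 per arm, the SE falls from 60·√(0.2·0.8) = 24.0 to 60·√(0.2·0.34) = 15.6 min.

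Power for a steady 45 min, σ = 60, mean 360 min:

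| Analysis | n = 10; ρ = 0.4 / 0.6 / 0.8 | n = 8; ρ = 0.4 / 0.6 / 0.8 |
|---|---|---|
| Percent change to week 4 | 0.28 / 0.40 / 0.66 | 0.22 / 0.32 / 0.55 |
| 4-df group-by-week | 0.28 / 0.42 / 0.74 | 0.23 / 0.33 / 0.62 |
| Adjusted mean, weeks 1–4 | 0.72 / 0.77 / 0.93 | 0.60 / 0.66 / 0.86 |

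**Step 3, a second set of assumptions, with selection.** Baseline week below 420 min, mean 390, between-person SD 45, SD of a weekly mean w = 25 or 35 min, 10 per arm, full 45 min from week 1 (simulated, except the omnibus test):
- Percent change to week 4: 77% / 49%.
- Omnibus: the half-difference profile (0, 22.5, 22.5, 22.5, 22.5) has mean 18, so λ = 20(18² + 4·4.5²)/w² = 8100/w² = 12.96 / 6.61. F(4,72) gives 81% / 48%.
- Adjusted mean of weeks 1–4: 95% / 81%. Its SE is 11.6 / 15.0 min, against 15.3 / 20.9 for raw change to week 4. The variance ratios are (15.3/11.6)² = 1.7 and (20.9/15.0)² = 1.9.

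**Step 4, gradual effect.** Let the gain build linearly: 11.25, 22.5, 33.75, 45 min. The four-week average is then 28.1 min, and 28.1/11.6 = 2.42, 28.1/15.0 = 1.87.
- Adjusted mean of weeks 1–4: 63% / 42%.
- Percent change to week 4: 76% / 48%. The week-4 effect is unchanged, so the gap from 77% / 49% is simulation error.
- Baseline-adjusted week 4: 79% / 55%.

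Unadjusted raw change to week 4 has 45/15.3 = 2.94 and 45/20.9 = 2.15, or about 79% / 53%. In this setting most of the small week-4 gain therefore comes from leaving the percent scale. Adjustment itself matters more at lower correlation: 0.39 / 0.49 / 0.73 adjusted, against 0.31 / 0.43 / 0.71 for raw change, at ρ = 0.4 / 0.6 / 0.8 in the setting of step 2.

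**The case against.** **A workable reading exists.** Percent change may be only how results are expressed, with weekly values going into the ANOVA. Weekly percent changes tested by the 1-df group effect would use all four intervention weeks and reach about 92% / 68% under step 3. So a reader who infers that the plan necessarily discards weeks 1–3 goes too far. But this is not what the sentence says, and it remains less precise than the adjusted model.

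**The gain depends on the time course.** This stands. Step 4 shows the ranking reversing. The one-week ramp mentioned under Alternative Strategies would only shrink the advantage: halving the week-1 effect leaves 89% / 69%. The four-week average is also a different quantity from sleep at the end of the period, when the final blood sample is drawn.

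**Regression to the mean.** The visit details exclude on the baseline week itself ("If the subject's average sleep duration is not below 7 hours per night"), so a reader might infer that percent change biases the comparison. It does not. Both arms are selected alike and randomised afterwards, the drift cancels, and simulated type I error is about 5%. It matters only for change within an arm: controls drift up about 6–11 min under step 3, or 4–17 min if the assumed mean runs from 370 to 420. Study Methods, moreover, selects on self-reported sleep.

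**Dropouts.** A reader might infer that a mixed model rescues them. Weeks 1–4 are downloaded only at the final visit, so it helps only with intermittent missing weeks or recovered watches.

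**Minutes.** Weekly means in minutes and descriptive statistics are planned, so minutes will be available. What is missing is a planned group difference in minutes with an interval.

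**It is a feasibility pilot with no power claim.** True, and this limits the severity. Power serves here only as a yardstick for precision.

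**Conclusion.** The point holds as a cheap improvement that should be made. Three statements need no assumed values: a beginning-to-end percent change leaves no repeated factor, no between-group contrast is named for H1, and baseline-week sleep is not used for adjustment.

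The size is conditional on inputs the documents do not give. For a steady effect and equal correlations of 0.4 to 0.8, raw change to week 4 has 1.9 to 3.1 times the variance of the adjusted four-week mean. Under step 3, power rises from about 77% / 49% to 95% / 81%. For a linear build-up the four-week average loses power, and adjusting at week 4 brings only a small gain over percent change.

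The documents do not support a stronger conclusion, that the planned comparison is biased or that the pilot cannot proceed without the change. The harm is an unspecified and probably imprecise estimate.

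**What to change.** Replace the sleep sentence with, for example:

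*Weekly mean total sleep time in minutes (weeks 1–4) will be analysed with a linear mixed model containing group, week, group-by-week and baseline-week sleep time. The main estimate is the group difference averaged over weeks 1–4 with its 95% CI; the week-4 difference from the same model is also reported. Every randomised participant with any post-randomisation week is included.*

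The other sleep components can use the same model, and percent change can stay as a descriptive summary. The covariance structure should be named in advance. With complete data the main contrast corresponds to ANCOVA on the four-week mean, so the figures above apply.

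The cost is one sentence and standard software, with no new data or visits. The downside is that the main quantity becomes a four-week average rather than end-of-period sleep, which is why week 4 is reported alongside.

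The two descriptions of 10 per arm should be reconciled at the same time. Ten recruited with 20% loss leaves 8; ten analysed needs 10/0.8 = 12.5, or 13 recruited per arm.

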
the fidelity of the intervention, we are including a sleep hygiene test that will be given at 3 time points: as a pre-test, and as a post-test immediately after the education and at the end of the 4-week intervention period. The researcher-developed sleep hygiene questionnaire is based on the sleep hygiene recommendations from the NSF and the American Academy of Sleep Medicine (AASM). Participants will identify true or false if an item is recommended to facilitate sleep. Non-sleep hygiene items will be included. In addition, the control group will receive an investigator-developed instrument with the list of safety practices based on safety information they receive. Both instruments will be reviewed for content validity by a content expert and researcher with measurement expertise. **Physical activity and Dietary characteristics:** Physical activity will be measured by activity levels from the actigraphy monitor as well as self-report using the Baecke questionnaire (Baecke, Burema & Frijters, 1982). Dietary habits will be measured by self-report using the 26-item Dietary Screener (National Cancer Institute, 2015). Both the Baecke questionnaire and Dietary Screener have evidence of validity (Philippaerts, Westerterp, & Lefevre 1999; Thompson et al, 2005). Diet and physical activity are also reported to impact IR, and a recent study found that in adolescent girls, poorer diet and lower physical activity were associated with higher levels of IR (Jiménez-Pavón et al, 2013). Measuring this at baseline and after the 4-week intervention period will allow us to assess if dietary and/or physical activity were mediators between sleep duration and IR. **Adherence to the intervention:** The percent of days extending time in bed will be computed from the total number of days TIB was actually extended by one hour over the total intervention days (4 weeks = 28 days). **Exit Interview:** Participants in both groups will be interviewed after the 4-week intervention period. This investigator-developed interview will assess their satisfaction with the intervention, any difficulties implementing the intervention strategies and what they felt was most effective and if they would recommend others to participate in the intervention. The interview questions will be reviewed by a content expert and researcher with measurement expertise. **Participant Characteristics:** Will be assessed at baseline via an investigator-developed questionnaire which will include T2DM risk factors based on the ADA risk assessment tool [male gender, family history of diabetes, high blood pressure, and physical inactivity (ADA, Are you at risk?)]. Additional data will include age, marital status, and factors that may affect sleep and/or glucose/insulin levels such as work hours, health problems, and medications. Calculation of BMI from height (stadiometer) and weight (calibrated scale) using a standard formula will be obtained. These data will describe the sample, and a total T2DM risk factor score will be calculated by summing the number of risk factors. Other data will be evaluated as potential covariates. BMI will be assessed at screening and at the end of the 4 week intervention period in both groups.

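### Aim 4 asks whether diet and physical activity mediate the link between sleep duration and IR, but the Analysis Plan contains no sleep-to-mediator model and no indirect effect, and its IR regression is large for 16–20 people

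*Combined protocol and SAP*

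**What the plan says.** In the combined protocol and SAP, Objectives gives Aim 4 as to "explore the potential mediators of diet and physical activity between sleep duration and IR". Outcome Measures repeats the intent: collecting these data at baseline and after the 4 weeks "will allow us to assess if dietary and/or physical activity were mediators between sleep duration and IR".

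For IR, the Analysis Plan names three things: percent change in blood levels, a correlation ("Correlational analysis will be used with sleep variables and IR") and a regression ("Regression analysis including components of sleep, BMI, dietary and physical activity will be conducted to examine the association of sleep factors and IR"). A separate model covers sleep as an outcome: "Sleep characteristics will be expressed as percent change from beginning to end and analyzed with repeat measures ANOVA". The section does not mention mediation. It has no model with diet or activity as the response, no indirect effect and no interval for one. It also does not say whether IR enters the regression as a level or a change, or which of the two BMI measurements is used.

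The candidate predictors come from Outcome Measures:
- Sleep: the actigraph dimensions named are "sleep onset latency, wake time after sleep onset, total sleep time (sleep duration), and sleep efficiency percentage".
- Activity: "Physical activity will be measured by activity levels from the actigraphy monitor", with the Baecke questionnaire as a second source.
- Diet: a 26-item screener whose scoring is not described.
- Further participant characteristics may be considered as covariates.

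The Sample size paragraph under Procedures sets 10 per group with 20% attrition already allowed for. Sample/Setting under Study Methods speaks of a final 20.

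**The concern.** A mediation question needs two relations: exposure to mediator, and mediator to outcome given the exposure. It also needs a summary that combines them. The Analysis Plan covers only the second relation, inside a regression whose stated purpose is the sleep–IR association.

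Read alone, the sleep coefficient from that regression is the part of the association that does not pass through diet or activity. If the whole effect ran through them, the coefficient would be near zero and could be taken to mean that sleep does not matter for IR.

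The regression also asks a lot of a very small sample. Several overlapping sleep measures, BMI, diet and one or two activity measures would compete for the information in 16 to 20 people, so a sizeable raw R-squared is expected by chance.

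**Working it through.** **Sample size.** The plan's own figure is 20 enrolled with 20% attrition: 20 × 0.8 = 16 completers, and 16 / 0.8 = 20, so the figure is consistent with itself. If the final 20 in Sample/Setting means completers, enrolment would be 20 / 0.8 = 25. No alpha, power, effect size or SD is given, so 20 cannot be derived from a power formula. I use N = 16 and N = 20.

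**Number of predictors (assumed, because the plan does not fix it).**
- Minimum 5: two sleep components (the plural implies at least two) + BMI + diet + one activity measure.
- Maximum 8: four sleep dimensions + BMI + diet + two activity measures, before any further covariates.

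**Overfitting.** With no true association, expected R-squared = p / (N − 1). Residual df = N − p − 1.

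| p | N | People per predictor | Residual df | Expected R-squared from noise |
|---|---|---|---|---|
| 5 | 20 | 4.0 | 14 | 5/19 = 0.26 |
| 5 | 16 | 3.2 | 10 | 5/15 = 0.33 |
| 8 | 20 | 2.5 | 11 | 8/19 = 0.42 |
| 8 | 16 | 2.0 | 7 | 8/15 = 0.53 |

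At an assumed two-sided alpha of 0.05 (noncentral F), a single coefficient reaches 80% power only for a partial correlation of about 0.61–0.63 (N = 16) or 0.56–0.57 (N = 20).

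**What the regression estimates.** Let a be the sleep-to-mediator path, b the mediator-to-IR path given sleep, and c′ the direct effect. Then total effect = c′ + a × b. Under assumed full mediation with a = b = 0.5 and c′ = 0, the total effect is 0.5 × 0.5 = 0.25. In a large simulated sample the sleep coefficient was 0.25 without the mediator and 0.00 with it. The regression therefore estimates c′ and b. Nothing in the plan estimates a, so a × b is not available.

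**Can the correlation fill the gap?** In linear models with identical covariates, total minus direct equals a × b. The planned correlation is unadjusted and on a different scale. The regression also conditions on BMI and other sleep components. The difference between the two is therefore not the indirect effect through diet or activity.

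**What a complete analysis could deliver.** I used 20,000 simulated trials per setting and the joint-significance test of a and b. Assumptions: one mediator, a = b (standardised), no direct effect, alpha 0.05.

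| Assumed a = b | Sleep as exposure, N = 16 / 20 | Group as exposure, N = 16 / 20 |
|---|---|---|
| 0.30 | 3% / 5% | 3% / 5% |
| 0.39 | 8% / 13% | 8% / 14% |
| 0.50 | 20% / 31% | 22% / 33% |
| 0.59 | 35% / 51% | 38% / 54% |

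With sleep as the exposure and paths of 0.39, N = 70 gives about 81% (8,000 simulated trials).

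**The case against.** The strongest reply is that a model of IR on sleep and the mediators is a legitimate part of a mediation analysis, that Aim 4 is only exploratory, and that the aim is neither of the two hypotheses. All of that stands. A reader might infer that the planned regression is the opposite of what Aim 4 needs. It is not: it is one half, and the fault is that the other half is missing.

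Four other strong readings are tempting, and the documents do not support them.
- **The regression has seven or eight predictors.** The four sleep dimensions come from a sentence on validating the device, not from a list of model terms, and the wording of the Analysis Plan does not fix a single model. Five to eight is an assumption. At five the model is still large for the sample.
- **The missing group term defeats Aim 4.** The aim's exposure is sleep duration, not arm. Not naming group bears mainly on H2 ("A greater proportion of the SLEEP-Extend group will have a decrease in IR compared to the control group") and on causal interpretation. Even with group as the exposure, the mediator-to-IR path is not randomised.
- **Actigraph activity would look like a mediator by construction.** This holds only in part, and only if a 24-hour total is used, which the plan does not say. With an assumed 6.5 h of baseline sleep, one more hour asleep removes 1 / (24 − 6.5) = 5.7% of waking time. That affects only the sleep-to-activity path. Apparent mediation also needs activity to predict IR given sleep.
- **Chance mechanisms would shape the next trial.** Introduction and Background rests the larger study on feasibility, longer sleep and preliminary IR improvement, not on mediation results.

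It is also fair to say that adjusted R-squared has a null expectation of zero and that coefficient tests allow for residual df. The practical cost is imprecision and the risk of selective reading, rather than an invalid test.

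**Conclusion.** The point holds in a limited form. The document commits twice to assessing mediation, and the Analysis Plan contains no mediator model, no indirect effect and no interval. Followed as written, it leaves Aim 4 unanswered.

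The IR regression is also too large for the data. Noise alone gives an expected R-squared between 0.26 (5 predictors, 20 people) and 0.53 (8 predictors, 16 people), on 7 to 14 residual df. These figures rest on the assumed predictor range and on reading 20% attrition as 16 completers.

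The correction makes the aim estimable but not testable in any useful sense. About 20–33% power at assumed paths of 0.5 means that an absent signal would say little. The aim is exploratory, so this should be corrected before analysis, but it does not threaten the main comparisons.

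**What to change.** For Aim 4, replace the multi-predictor regression with models for one mediator at a time. Use change in mean total sleep time as the only sleep exposure, and state which weeks define the change:

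- (a) change in the mediator on change in sleep time;
- (b) log end-of-study HOMA-IR on change in sleep time, log baseline HOMA-IR and that mediator's change;
- (c) model (b) without the mediator, and without end-of-study BMI, for the total effect.

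Report the indirect effect (the product of the sleep coefficient in (a) and the mediator coefficient in (b)) with a bootstrap 95% interval, labelled descriptive. Add a version with randomised group as the exposure as a supporting analysis. If actigraph activity is used as a mediator, express it per waking minute, so that longer sleep does not lower it mechanically. Also state whether 20 means enrolled or completing.

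Model (b) has three predictors, leaving 16 − 3 − 1 = 12 to 20 − 3 − 1 = 16 residual df.

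The cost is Analysis Plan wording only, because HOMA-IR, sleep, diet and activity are already measured at both times. There are two downsides. Sleep components other than total sleep time are no longer examined in the IR model, and the indirect effects will have wide intervals that support no more than an exploratory statement.
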